8.2 Randomisation, blinding and treatment allocation

Subject randomization will take place before the start of administration of the IMP.

Subjects will be randomized in a 1:1:1 ratio to the three treatment arms and stratified by site.

Randomization of the subjects will be performed by an Interactive Web-based Randomization System (IWRS) by an independent party. The randomization number will be recorded on the eCRF. Once the numbers have been assigned they cannot be reassigned.

Subjects in this trial will be randomized in a 1:1:1 ratio to receive one of three dose groups:

- **Nanocort 75 mg** IV infusion and IM saline injection on Day 1 and Day 15, or
- **Nanocort 150 mg** IV infusion and IM saline injection on Day 1 and Day 15, or
- **Depo-Medrol 120 mg** IM injection and IV saline infusion on Day 1 and Day 15

Blinding:

Prior to the start of the study, a copy of the master randomization code will be stored in confidential manner up to the unblinding after database lock. A separate unblinded Pharmacovigilance Medical Reviewer and unblinded Pharmacovigilance Associate will be available for triage, review and submission of safety events.

Any reported Suspected Unexpected Serious Adverse Reactions (SUSARs) will be triaged by the Medical Monitor in a blinded fashion and forwarded for full processing to the unblinded Medical Reviewer and unblinded Pharmacovigilance Reviewer for processing and reporting to the Competent Authority (CA) and Independent Ethics Committee (IEC) per regulations.

Unblinding to Investigator and subject will occur only after database closure at the end of the study. The study blind will only be broken after database lock except in the case of

emergency to protect subject's safety. The code may be broken in case of an emergency, preferably after discussion with the MM. Any code break will be recorded and a copy retained within the study file.

The blind will be preserved throughout the study unless, in the opinion of the Investigator, the lack of this information places the subject at undue risk. In general, this will occur only if an adverse event occurs for which the subject's physician requires knowledge of the treatment assigned. In this case, the Sponsor should be notified as soon as possible and un-blinded information for the subject's treatment group will be provided.

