10.4.7 Quality of Life and RA activity questionnaires

Short Form 36 (SF-36) to assess physical and mental component at Baseline and Week 1, 2, 4, 6, and 12. Pair-wise comparisons of absolute changes from Baseline at Weeks 4, 6 and 12 will be performed using Analysis of covariance (ANCOVA), with study site, SF-36 score at Baseline DAS28 level, age and gender as covariates.

The Health Assessment Questionnaire (HAQ) at every visit (except Screening visit). Pair-wise group comparisons of HAQ score changes from Baseline at Weeks 3, 6 and 12 will be analyzed by ANCOVA, with study site, Baseline DAS28 level and HAQ score at baseline as covariates.

The Functional Assessment of Chronic Illness Therapy (FACIT) at Baseline, Week 4 and 6. The pair-wise comparisons between treatment groups of the changes from Baseline in FACIT-Fatigue scores will be performed by using ANCOVA with study site, Baseline DAS28 level and Baseline FACIT score as covariates.

For the ANCOVA analyses, least squares means and the pairwise comparisons between treatment groups in adjusted least-squares means with their Tukey 95% CIs will be presented.

Descriptive statistics for the surveys /questionnaires will be presented.

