1.1 Study Population

The study has been conducted at 21 sites in the Netherlands and Belgium. Sites were selected based on previous study experience in RA and accessibility to study required populations. The study population will consist of male and female subjects (≥ 18 years old) with active RA who are experiencing a flare / exacerbation defined as a recent increase in symptoms and a measured increase in DAS28 > 1.2 or > 0.6 if DAS28 ≥ 3.2 despite disease-modifying anti-rheumatic drugs (DMARDs) therapy or treatment naïve patients compared to last DAS28 measurement (maximum 6 months before screening).

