2.4 Safety Population

The safety population (SAF) will include all patients who receive at least one infusion or part of infusion with Nanocort/placebo or at least one IM injection or

part of IM injection with Depo-Medrol/placebo and had at least one post baseline safety assessment.

Patients will be assigned to treatment groups as treated for analysis.

3. Blinded Review of the Data

A blinded data review will be held before breaking the blind. The blinded data review will be performed by at least the Principal Investigator, the Medical Monitor, the Study Lead and the Trial Statistician. The goal of the blinded data review is to determine for each subject the maintenance of improvement at 12 Weeks, the protocol violations and to evaluate the impact of these protocol violations on the EULAR response.

The decisions taken during the blinded data review will be finalized and signed by participants on the blinded data review report before unblinding.

4. Statistical and Analytical Methods

This analysis plan gives a detailed description of the statistical methodologies, data listings, and summary tables planned in the analysis of the data in the CLR-15-05 study. This section describes the statistical analyses of the study based on the statistical section of the protocol (CLR15_05_Prot_V3.1_Amend_25Sep2017.pdf). Any difference with the protocol will be identified and documented. The statistical data analysis, described in this document, is intended to provide unbiased and valid conclusions concerning the objectives of the study.

This SAP describes only the analyses for the study objectives not involving the PK objectives. The PK objectives will be described in a separate analysis plan.

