Short Form 36 (SF-36) to assess physical and mental component at baseline, week 1, 2, 4, 6, and 12 will be summarized and analyzed. See Appendix A for details on scoring and coding. If the change from baseline is approximately normally distributed via visual inspection, then the change from baseline at 1, 2, 3, 4, 6, 8 and 12 weeks will be analyzed using ANCOVA, including baseline scores, age and gender as covariates. If the change from baseline is markedly non-normally distributed via visual inspection, then the Kruskal-Wallis test will be used to compare the groups at each time point.

Health Assessment Questionnaire (HAQ) at baseline, week 1, 2, 3, 4, 6, 8 and 12 will be summarized and analyzed. See Appendix E for details on scoring and coding. If the change from baseline is approximately normally distributed via visual inspection, then the change from baseline at 1, 2, 3, 4, 6, 8 and 12 weeks will be analyzed using ANCOVA, including baseline HAQ, baseline DAS28 and study site as covariates. If the change from baseline is markedly non-normally distributed via

visual inspection, then the Kruskal-Wallis test will be used to compare the groups at each time point.

FACIT Fatigue Scale at baseline, week 4 and 6 will be summarized and analyzed. See Appendix F for details on scoring and coding. If the change from baseline is approximately normally distributed via visual inspection, then the change from baseline at 1, 2, 3, 4, 6, 8 and 12 weeks will be analyzed using ANCOVA, including baseline FACIT, baseline DAS28 and study site as covariates. If the change from baseline is markedly non-normally distributed via visual inspection, then the Kruskal-Wallis test will be used to compare the groups at each time point.

Maintenance of Improvement at 12 Weeks assessed during a blinded review by the Medical Monitor (MM) and Principal Investigator (PI) at the end of the study will be compared between treatment groups using a stratified Cochrane-Mantel-Haenszel test, stratified by study site.

The Health Economics Questionnaire (HEQ) at week 12 will be summarized in a table of the responses for each treatment group as recorded on the questionnaire.

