4.11 Modifications from the statistical section in the protocol

The protocol stated hypotheses with one-sided testing using less than and greater than symbols. This is corrected in the SAP to two-sided hypotheses, as planned, using equal and not equal symbols.

The protocol stated that Cochrane-Mantel-Haenszel test stratified by study site will be used for the primary analysis. However, this conflicts with the primary and key secondary hypotheses planned in the protocol which are not stratified, so this is revised in the SAP to match with the planned hypotheses.

Due to early termination of the study, the sample size will be much less than planned. As a result, the statistical power can be inadequate for the planned

gatekeeping methodology. Therefore, standard hypothesis testing methods may be used instead to analyze the data (see section 4.8).

5. Interim analyses

No interim analyses were planned.

6. Sample size and Power calculations

A total of 330 subjects were to be enrolled and randomized into 3 groups (1:1:1).

The EULAR response rate will be considered as primary parameter. See Appendix B for details on scoring and coding. There is a special interest in the percentage of subjects with an EULAR response category of good or moderate (good and moderate combined) and the percentage of subjects with an EULAR response category of only good. These subjects will be called EULAR responders and EULAR good-responders, respectively.

[figure not shown]

Primary endpoint:

- The percentage of EULAR responders (good + moderate) at Day 8

Key secondary endpoints:

- The percentage of EULAR good responders at Day 8
- The percentage of EULAR responders at Day 15
- The percentage of EULAR good responders at Day 15

[REDACTED]

[REDACTED]
[REDACTED]
[REDACTED]
[REDACTED]
[REDACTED]
[REDACTED]

The sample size calculation is based on estimates from [REDACTED]

[REDACTED]
[REDACTED]
[REDACTED]
[REDACTED]
[REDACTED]
[REDACTED]
[REDACTED]
[REDACTED]
[REDACTED].

Although the above described the planned sample size, the study enrollment did not reach the planned goal, and the study may likely have inadequate statistical power.

7. Tables, Listings and Figures

Below are the titles for the planned study tables, listings and figures

Table 1	Subject Distribution
Table 2.A	Subject Distribution By Center (ITT)
Table 2.B	Subject Distribution By Center (PP)
Table 3.A	Demographics and Baseline Characteristics (ITT)
Table 3.B	Demographics and Baseline Characteristics (PP)

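### The SAP's SF-36 ANCOVA leaves out study site and, on the natural reading, baseline DAS28, which the protocol specifies, and does not record the change

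*Combined protocol and SAP*

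**What the plan says.** Protocol 10.4.7 compares SF-36 change from baseline pairwise at Weeks 4, 6 and 12 by ANCOVA, "with study site, SF-36 score at Baseline DAS28 level, age and gender as covariates". For the same endpoint, SAP 4.8.3 says that change "will be analyzed using ANCOVA, including baseline scores, age and gender as covariates", at weeks 1, 2, 3, 4, 6, 8 and 12.

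The next two paragraphs of SAP 4.8.3 treat the sister questionnaires differently: HAQ is modelled "including baseline HAQ, baseline DAS28 and study site as covariates" and FACIT "including baseline FACIT, baseline DAS28 and study site as covariates". The DAS28 and VAS ANCOVAs in that section also keep study site.

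On design, protocol 8.2 states: "Subjects will be randomized in a 1:1:1 ratio to the three treatment arms and stratified by site". On departures, SAP section 4 undertakes: "Any difference with the protocol will be identified and documented". SAP 4.11 then lists three changes: the sidedness of the hypotheses, the site stratification of the primary test, and the response to early termination. The only entry about site begins "The protocol stated that Cochrane-Mantel-Haenszel test stratified by study site will be used for the primary analysis" and explains that stratification was removed to match the primary and key secondary hypotheses. SF-36 is not mentioned.

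**The concern.** Two documents give two models for one endpoint, and no reason is recorded. SF-36 serves the patient-reported-outcome objective (protocol section 2, SAP 1.3.2), so the model should be settled before unblinding.

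Two statistical matters are involved. First, when randomisation is stratified by a factor that predicts outcome and the model ignores that factor, the estimated standard error still contains between-site variation that the design has largely balanced out. Intervals are then wider than they need be. Second, a prognostic baseline covariate that is already collected is left unused. Either could cost precision in a trial that the SAP itself expects to be underpowered. Whether it does depends on how many subjects there are per site.

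**Working it through.** **Step 1: compare the covariate lists.**

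| Model | Baseline score | Study site | Baseline DAS28 | Age, gender |
|---|---|---|---|---|
| Protocol 10.4.7, SF-36 | yes | yes | yes, if a comma is supplied | yes |
| SAP 4.8.3, SF-36 | yes | **no** | **no** | yes |
| Protocol 10.4.7, HAQ and FACIT | yes | yes | yes | no |
| SAP 4.8.3, HAQ and FACIT | yes | yes | yes | no |
| SAP 4.8.3, VAS | yes | yes | no | no |
| SAP 4.8.3, DAS28 | yes | yes | is the baseline score | no |

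SF-36 is the only ANCOVA endpoint in the SAP without site. The absence of site needs no interpretation. The absence of baseline DAS28 depends on reading a comma into the protocol's phrase, which has no sensible meaning otherwise; the protocol's HAQ and FACIT models name baseline DAS28 separately.

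**Step 2: check the visits.** Protocol 8.3 collects SF-36 at baseline and Weeks 1, 2, 4, 6 and 12. The SAP's list adds weeks 3 and 8, when there are no data. The same seven-week list appears for FACIT, which is collected only at baseline and Weeks 4 and 6, so it looks like carried-over text.

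**Step 3: count the parameters.** SAP 1.1 gives the number of sites: "The study has been conducted at 21 sites in the Netherlands and Belgium". As fixed effects these use 21 − 1 = 20 degrees of freedom; baseline DAS28 uses 1. The SAP model has 1 + 2 + 3 = 6 parameters (intercept, two treatment terms, three covariates). The protocol model has 6 + 1 + 20 = 27. At the planned 330 subjects (330/21 = 15.7 per site) residual degrees of freedom fall from 324 to 303. At an assumed 60 (60/21 = 2.9 per site) they fall from 54 to 33.

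**Step 4: simulate both models.** The documents state no precision figure for SF-36, so there is none to reproduce. Inputs from the documents are three arms at 1:1:1, stratification by site, 21 sites and a planned 330 subjects. Assumptions are permuted blocks of 6, unequal site sizes, no treatment effect, and age and gender not prognostic. Of the variance left after the baseline score, site takes 0, 5, 10 or 20% and baseline DAS28 takes 0, 5 or 10%. There were 1,000 runs per scenario and 12 scenarios per sample size. The table gives mean 95% interval half-width, protocol model divided by SAP model; below 1 favours the protocol model.

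| N | Site 5%, DAS28 5% | Range over 12 scenarios | Scenarios above 1 |
|---|---|---|---|
| 60 | 1.080 | 0.951 to 1.135 | 10 |
| 100 | 1.005 | 0.888 to 1.058 | 6 |
| 150 | 0.978 | 0.864 to 1.028 | 3 |
| 330 | 0.956 | 0.849 to 1.007 | 1 |

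At 330 the single value above 1 is the scenario where neither factor matters; the other eleven lie between 0.849 and 0.984.

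**Step 5: check validity.** Against a nominal 5%, with Monte Carlo standard error √(0.05 × 0.95/1,000) = 0.7 percentage points, the SAP model rejected in 1.9 to 4.4% of runs when site took 20% of variance and in 3.3 to 5.7% otherwise. There is no sign of inflation, and the test is conservative when sites differ strongly.

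**Step 6: separate the two effects, at N = 330.** With site at 20% and DAS28 at 0, the half-width ratio is 0.908 but the ratio of the actual standard deviations of the estimates is 0.995. The estimate is about equally good under both models; the SAP model merely reports too large an error. With DAS28 at 10% and site at 0, the two ratios are 0.955 and 0.958, which is a real gain.

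**The case against.** The strongest objection is that dropping site may suit a trial that stopped early. The SAP expects far fewer subjects than planned, and 20 fixed site terms can cost more than they explain. As a limit on any precision claim, this stands. It does not explain the SAP: the same sparsity affects HAQ, FACIT, DAS28 and VAS, which all keep site, and it gives no reason to drop baseline DAS28, which costs one degree of freedom.

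Different covariate sets are not in themselves a defect. The protocol gives age and gender to SF-36 alone. That stands too; the point rests on the unrecorded departure, with the sister models as supporting evidence.

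There are also source caveats. The baseline DAS28 part needs the comma. The SAP cites protocol V3.1, and the protocol shown cannot be confirmed as that version: SAP 4.11 describes one-sided protocol hypotheses, while protocol 4.4 states equalities. The departure might therefore be from a different text.

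A reader might infer that the SAP model simply loses precision. Under an assumed 5 to 15% of residual variance explained, 1/√(1 − R²) − 1 gives standard errors 2.6 to 8.5% larger. The documents do not support this as an unconditional statement. They give no value for R², the formula charges nothing for the site terms or the lost residual degrees of freedom, and at small N the direction can reverse.

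**Conclusion.** The discrepancy is real on the documents shown: study site certainly, and baseline DAS28 on the natural reading, are missing from the SAP's SF-36 model with no entry in 4.11. It is a possible loss of efficiency and a documentation fault. A reader might also infer that ignoring the stratum biases the comparison or makes the test liberal; neither follows, and the simulation shows a conservative test if anything.

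The size cannot be fixed from the documents because the achieved sample size is not given. Under the simulation's assumptions, restoring both terms with site as fixed effects narrows intervals by about 2 to 15% at 330 subjects if either factor is prognostic, and usually widens them at 60, by up to about 14%. Pooling sites or treating site as random is meant to limit that cost; neither was simulated.

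Severity is low. SF-36 is among the other secondary analyses, outside the primary and key secondary testing scheme, and the primary conclusion is unaffected.

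**What to change.** - Restore baseline DAS28 and study site in the SF-36 ANCOVA, alongside baseline SF-36 component score, age and gender.
- Either pool small sites by a rule fixed before unblinding, for which the blinded data review in SAP section 3 is a natural place, or fit site as a random effect. Handle site the same way for HAQ and FACIT.
- Fit the model only at weeks when SF-36 is collected: 1, 2, 4, 6 and 12, not 3 and 8. The protocol's pairwise comparisons are at Weeks 4, 6 and 12 only, so comparisons at Weeks 1 and 2 would be additions and should be labelled as such.
- List any remaining departure in SAP 4.11 with its reason. If the sponsor prefers the SAP's model, that entry is the minimum needed.

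The cost is a line or two of the SAP and the pooling rule, plus one degree of freedom for baseline DAS28 and up to 20 for site if it is fixed and unpooled, fewer if pooled. No new data are needed.

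### SAP 4.8.3 departs from protocol 10.4.7 on the HAQ, SF-36 and FACIT comparisons (tested weeks, Tukey intervals, SF-36 covariates), and SAP 4.11 does not record it

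*Combined protocol and SAP*

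**What the plan says.** **Protocol 10.4.7.** For HAQ: "Pair-wise group comparisons of HAQ score changes from Baseline at Weeks 3, 6 and 12 will be analyzed by ANCOVA". SF-36 gets the same kind of pairwise comparison at Weeks 4, 6 and 12. FACIT is given as "The Functional Assessment of Chronic Illness Therapy (FACIT) at Baseline, Week 4 and 6", with pairwise comparisons of the changes from baseline. For all these ANCOVAs, the "pairwise comparisons between treatment groups in adjusted least-squares means with their Tukey 95% CIs will be presented". The SF-36 covariates are study site, baseline SF-36, baseline DAS28, age and gender. A comma seems to be missing between the baseline SF-36 score and the DAS28 level. The HAQ and FACIT lists in the same section name baseline DAS28 as a covariate of its own, so I read it that way here.

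**SAP 4.8.3.** For HAQ: "the change from baseline at 1, 2, 3, 4, 6, 8 and 12 weeks will be analyzed using ANCOVA, including baseline HAQ, baseline DAS28"; the model also adjusts for study site. The same seven-week list stands in the SF-36 and FACIT paragraphs. The FACIT paragraph nevertheless opens with "FACIT Fatigue Scale at baseline, week 4 and 6 will be summarized and analyzed", and the SF-36 paragraph opens with Weeks 1, 2, 4, 6 and 12. The SF-36 covariates are now baseline scores, age and gender. If the data look clearly non-normal, a Kruskal-Wallis test at each time point replaces the ANCOVA. Neither pairwise comparisons nor Tukey intervals are mentioned for these instruments.

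**Record of changes.** The opening of SAP section 4 promises: "Any difference with the protocol will be identified and documented". SAP 4.11 lists three items: two-sided hypotheses, the unstratified primary test, and the effect of early termination.

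**The concern.** Patient-reported outcomes under Nanocort compared with Depo-Medrol are the first secondary objective in both documents. The protocol limited the chance findings on them in two ways: it named the weeks to be compared, and it adjusted for the three pairs of arms within each week. The SAP text keeps neither limit.

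Two things are at stake. First, more visits are tested, so a nominal difference at some visit is more likely when there is no effect. A reader who relies on 4.11 would not learn that the protocol had named only three weeks. Second, a single three-group ANCOVA test or a Kruskal-Wallis test gives no Nanocort-versus-Depo-Medrol estimate, which is what the objective asks for. Read as pairwise, the SAP names no adjustment. The text needs correcting on either reading.

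**Working it through.** The documents give no error rate for these tests, so there is no stated figure to reproduce.

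**Step 1. Weeks named, ordered and collected** (collection schedule from protocol 8.3)

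| Instrument | Protocol comparison weeks | SAP ANCOVA weeks | Collected after baseline | Ordered but not collected |
|---|---|---|---|---|
| HAQ | 3, 6, 12 | 1, 2, 3, 4, 6, 8, 12 | all seven | none |
| SF-36 | 4, 6, 12 | same seven | 1, 2, 4, 6, 12 | 3, 8 |
| FACIT | 4, 6 (weeks measured) | same seven | 4, 6 | 1, 2, 3, 8, 12 |

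In practice HAQ goes from 3 to 7 tested weeks, SF-36 from 3 to 5 for each component, and FACIT stays at 2.

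**Step 2. Rules compared, with no true effect and three equal arms**

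- Protocol: at a named week, any of the three pairs exceeds the Tukey limit, |Z| > 2.344. This is 5% per week.
- SAP, reading A: one three-group test per visit at 5%.
- SAP, reading B: two unadjusted comparisons with Depo-Medrol per visit, |Z| > 1.960.

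**Step 3. Independent visits, in closed form (HAQ)**

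P(at least one) = 1 − 0.95^k. For k = 3 this is 1 − 0.8574 = 14.3%. For k = 7 it is 1 − 0.6983 = 30.2%. The ratio for reading A is 30.2/14.3 = 2.1, an upper end, because repeated HAQ scores in one patient are correlated.

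**Step 4. Correlated visits (HAQ), 40,000 null trials per setting**

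The correlations are assumptions; the documents give none.

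| Assumed visit correlation | Protocol | Reading A | A / protocol | Reading B | B / protocol |
|---|---|---|---|---|---|
| Decaying, 0.5 | 14.4% | 27.3% | 1.9 | 43.7% | 3.0 |
| Decaying, 0.7 | 13.6% | 23.6% | 1.7 | 37.7% | 2.8 |
| Decaying, 0.8 | 12.1% | 19.8% | 1.6 | 32.6% | 2.7 |
| Equal, 0.6 | 11.9% | 20.7% | 1.7 | 33.9% | 2.8 |
| Equal, 0.8 | 9.9% | 15.1% | 1.5 | 25.3% | 2.6 |

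The first protocol figure is above the independent value of 14.3% only through simulation error.

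**Step 5. All three instruments, a separate run of 200,000 null trials**

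Equal visit correlation 0.5; the two SF-36 components are assumed correlated at 0.3.

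| Instrument | Protocol | Reading A (ratio) | Reading B (ratio) |
|---|---|---|---|
| HAQ | 12.9% | 23.4% (1.8) | 38.2% (3.0) |
| SF-36, both components | 23.3% | 33.2% (1.4) | 51.6% (2.2) |
| FACIT | 9.1% | 9.1% (1.0) | 16.2% (1.8) |

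At correlation 0.7 the SF-36 ratios are 1.3 and 2.1. A test at a week without data cannot be run and adds nothing to any of these figures.

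**The case against.** The strongest reply is that the effect is modest and lies outside the confirmatory part of the trial. Much of that stands.

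- **The literal wording is the milder reading.** The SAP orders an ANCOVA or a Kruskal-Wallis test of the groups at each visit, which reads as one test per visit. It omits Tukey by silence and does not say that unadjusted pairs replace it. This stands. A reader might infer that chance findings become two to three times as likely overall, but the documents do not support that as a general statement.
- **The protocol did not control error across weeks or instruments either.** True: its Tukey intervals act within one week. Both documents also list HAQ at seven weeks and SF-36 at five as secondary endpoints. But the protocol separately chose which weeks to compare, and that choice is what was lost.
- **Many other secondary tests already run at every visit.** EULAR category, DAS28 (absolute and percentage change) and four VAS scores at seven visits make 7 × 7 = 49 analyses. The SAP change adds 4 for HAQ and 2 weeks × 2 components = 4 for SF-36. This lowers the weight of the point but does not explain an unrecorded change.
- **The uncollected weeks look like a copying slip.** Agreed. The opening sentences of the SF-36 and FACIT paragraphs largely resolve it, and SAP 4.2 presents available data only.
- **The protocol versions may differ.** The SAP cites an amended protocol version 3.1. SAP 4.11 describes hypotheses with inequality signs, while protocol 4.4 shows equalities. Redaction or another version could explain that, so the departure from the governing 10.4.7 is probable, not certain.

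**Conclusion.** The point holds as an unrecorded departure and a specification error in non-key secondary analyses. HAQ and SF-36 are outside the gatekeeping family, so the primary error rate and the criterion for a positive study are unaffected.

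For HAQ, with no true effect and assumed visit correlation of 0.5 to 0.8, the chance of at least one nominal difference is about 10-14% under the protocol. Under the SAP it is about 15-27% (1.5 to 1.9 times) with one three-group test per visit, or about 25-44% (2.6 to 3 times) with two unadjusted comparisons with Depo-Medrol. The rise is smaller for SF-36, and FACIT shows none on the three-group reading.

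Three stronger inferences are tempting but not supported:

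- That SF-36 is tested at every visit: only five post-baseline visits have data.
- That the empty weeks raise the false-positive rate: they cannot be tested.
- That a chance Nanocort benefit is likely: every HAQ figure is below one half, the tests are two-sided so about half of chance differences from Depo-Medrol would favour Depo-Medrol, and the three-group test also picks up differences between the two Nanocort doses.

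The SAP itself expects inadequate power after early termination, so an isolated nominal p-value at one visit would be hard to interpret.

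**What to change.** In SAP 4.8.3:

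- Restore the protocol comparisons: SF-36 at Weeks 4, 6 and 12; HAQ at Weeks 3, 6 and 12; FACIT at Weeks 4 and 6.
- For each, report the Nanocort-versus-Depo-Medrol adjusted mean differences with Tukey 95% CIs. State which between-arm estimate is reported if the Kruskal-Wallis fallback is used, since that test gives none.
- Restore study site and baseline DAS28 in the SF-36 model.
- Present the other collected weeks descriptively, and delete Weeks 3 and 8 for SF-36 and Weeks 1, 2, 3, 8 and 12 for FACIT.

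In SAP 4.11, list any departure from protocol 10.4.7 that is kept.

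The cost is SAP wording only. The downside is that the extra HAQ and SF-36 weeks carry no p-value.
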